#### Local AESI:

Local AESIs will be identified by one of the following conditions:

- Any adverse events with a preferred term (PT) corresponding to this prespecified list of PT according to the MedDRA version 20.1:
  - Application site abscess
  - Application site burn
  - Application site cyst
  - Application site discharge

CONFIDENTIEL / Ne pas diffuser sans autorisation de DBV

CONFIDENTIAL / Do not distribute without DBV authorization

	Statistical Analysis Plan	
	EPITOPE (V712-304) – Statistical Analysis Plan	
	Référence du Document /Document Reference : CCI	Page : 49 / 74

CCI

- Application site extravasation
- Application site fissure
- Application site haemorrhage
- Application site injury
- Application site laceration
- Application site necrosis
- Application site scab
- Application site scar
- Application site ulcer
- Application site vesicles
- Application site wound
- Any adverse events with verbatim which contains “GRADE 4 or “GRADE IV” for HLT = “Application and instillation site reactions”.

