**Table 1: List of Solicited Adverse Events (Applicable for Part B Only)**

Application site reactions	Systemic events of a potential allergic nature

 
• Pruritus
 
• Erythema
 
• Oedema
 
• Urticaria
 
• Hyperpigmentation
 
• Eczema
 
• Excoriation (erosion)
 
• Ulceration
 
• Blister (vesicles)
 
• Grade 4 patch site reactions (erythema with vesicles)
 
• Pain under the patch
 
	
 
• Asthma aggravation/exacerbation
 
• Hives
 
• Eyelid oedema
 
• Allergic contact conjunctivitis
 
• Lip swelling
 
• Angioedema
 

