#### 6.2.1.3.5 Adverse Events of Special Interest

Adverse Events of Special Interest (AESI) to the Sponsor are defined as follows:

**Local AESI:** Any reaction at patch application site which could potentially lead to a skin barrier disruption, such as but not limited to, blister, vesicle, ulcerative skin lesion, bleeding or any Grade 4 patch site reaction.

Skin reactions will be examined at the time points specified in the Schedule of Procedures (page 15) according to grading in Table 3 (Section 6.2.6). Subject's parents/guardians will be instructed to take a photograph in case of appearance of any vesicles or ulcerative skin lesions. In these rare specific cases, subjects should transiently discontinue patch application and return to the site for evaluation and treatment of the wounded area, as well as for the next patch application and adequate evaluation and treatment of the wounded zone.

Upon re-application of the new patch, the subject should remain at the site for 1 hour before being discharged. The site must contact the subject's parents/guardians by phone the day after this visit to ensure that no additional local blisters or vesicles developed and to confirm that the treatment can continue normally. The zone with vesicles or severe lesions should not be used for patch application until it has completely healed.

**Local AESI should NOT be reported on the specific AESI form of the eCRF.** This specific AESI form is only to be used for systemic AESI (see below).

**Systemic AESI:** Any acute systemic immediate allergic reactions (rapid onset) after exposure to a known or suspected allergen regardless of the causal relationship to the IMP, and occurring outside the DBPCFCs:

1. Anaphylactic reaction:

- Any AE diagnosed by physician as an anaphylactic reaction, regardless of the severity and causal relationship to the IMP.
- Anaphylactic reaction defined as the occurrence of the following allergic symptoms:
  - Major acute allergic reaction (associated or not with other symptoms): acute hypotension (>20% drop in blood pressure) or associated cardiovascular symptoms (hypotonia, confusion, loss of consciousness, collapse, syncope, incontinence);
  - 2 or more concomitant acute allergic symptoms from at least 2 different organ systems such as, but not limited to:
    - Upper airway or respiratory symptoms (dyspnea, wheeze-bronchospasm, stridor, hypoxemia, decreased SaO2)

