**Table 3: Skin Reaction Grading System**

Skin Reaction	Grade if localized under the patch	Grade if extending beyond the patch
Negative	Grade 0	Grade 0
Only erythema, or erythema and infiltration	Grade 1A	Grade 1B
Erythema and few papules	Grade 2A	Grade 2B
Erythema and many or spreading papules	Grade 3A	Grade 3B
Erythema and vesicles	Grade 4A	Grade 4B

The Viaskin® patch is transparent and the degree of the local reactions under the Viaskin® patch can be easily seen through the patch. Grading of the local skin reactions on the back will start being recorded at Visit 4 right after the Viaskin® patch has been applied and while the subject is kept at site under observation and subsequently when subjects return at site for their visits.

During Visit 4, the first Viaskin® patch will be applied at the study site for 2 hours. The patch will then be removed after 2 hours and all subjects will be observed for 1 additional hour before being discharged. The reactions under or around the patch will be checked and graded: before application, at 30 minutes, 1 hour, 2 hours during patch application and

then 1 hour after the patch removal, before subject discharge. Photographs will be taken at each grading time point.

[figure not shown]
Appearance of any vesicles (grade 4) or ulcerative skin lesions or any other significant skin lesion seen under the patch while the patch is still applied on the skin or upon removal of the patch which could potentially lead to skin barrier disruption at sites of Viaskin® patch applications will be cautiously managed and follow-up.

Children's parents or guardians will be instructed to take a photograph of the patch skin area at home in case of appearance of any vesicles or ulcerative skin lesions. In these rare cases, subjects should transiently discontinue the patch applications and return to the site for evaluation and treatment of the wounded area, as well as for the next patch application and adequate evaluation and treatment of the wounded zone.

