### 3.3 Safety Endpoints

The following IMP safety criteria will be evaluated:

- Treatment emergent adverse events (TEAEs) by System Organ Class (SOC) and Preferred Terms (PTs);
- TEAEs by maximum severity and relatedness to DBV712;
- Incidence, duration and maximum severity of local cutaneous DBV712-induced AEs as assessed by the subject in the diary;
- Incidence and severity of local cutaneous DBV712-induced AEs as assessed by the Investigator;
- Local adverse events of special interest (AESIs) (i.e., reactions at patch sites potentially leading to skin barrier disruption) and systemic AESIs (i.e. anaphylaxis, or systemic hypersensitivity reactions leading to epinephrine intake), whatever the causal relationship to the IMP;
- SAEs by SOC and PTs, and relatedness to DBV712;
- Laboratory data, physical examinations and vital signs;

The following study procedure safety criteria will be evaluated:

- Symptoms elicited during the entry/screening DBPCFC and post-treatment DBPCFC at Month 12 by severity;
- Change in severity of symptoms elicited during the DBPCFC from baseline to Month 12 in the selected active DBV712 group (250 µg) *versus* the placebo group;
- SAEs elicited during the entry/screening DBPCFC and post treatment DBPCFC at Month 12.

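### The SAP's closed list for local AESIs names no erosion or excoriation term, so a patch-site reaction the protocol solicits can fall outside the local AESI count

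*SAP*

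**What the plan says.** Protocol 6.2.1.3.5 gives an open definition of local AESI: "Any reaction at patch application site which could potentially lead to a skin barrier disruption, such as but not limited to", followed by five examples (blister, vesicle, ulcerative lesion, bleeding, any Grade 4 patch-site reaction). SAP 3.3 keeps the same concept as a safety endpoint: "reactions at patch sites potentially leading to skin barrier disruption".

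SAP 5.5.1.1 then makes it operational through two conditions: "Local AESIs will be identified by one of the following conditions". The first is "Any adverse events with a preferred term (PT) corresponding to this prespecified list of PT according to the MedDRA version 20.1", with 15 terms listed. The second begins "Any adverse events with verbatim which contains" and looks for Grade 4 or Grade IV among application-site reactions.

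Protocol Table 1 lists the application-site reactions solicited in Part B. One of the 11 items is "Excoriation (erosion"), shown separately from ulceration and from blister. Protocol 6.2.1.1 has these items solicited at every visit and phone contact in Part B, which is the part this SAP analyses.

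**The concern.** An open clinical definition has been turned into a closed term search, and an event that sites are told to ask about is not named in the search. Local AESI is a named safety endpoint for a patch worn daily for 12 months by children aged 1 to 3. SAP 5.5.1.3 gives it its own row in the TEAE overview and repeats that overview by subgroup. Readers will take the row as the rate of reactions that threaten the skin barrier. An event that meets the protocol definition but is coded to an unlisted term would be missing from it, and an omission of this kind can only lower the count.

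**Working it through.** No sample size, power or error-rate figure is involved, so the check compares terms and then looks for any other way into the count.

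**Step 1: the list.** The 15 terms, all prefixed application site, are abscess, burn, cyst, discharge, extravasation, fissure, haemorrhage, injury, laceration, necrosis, scab, scar, ulcer, vesicles and wound. None contains erosion or excoriation.

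**Step 2: protocol items against the SAP rule.**

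| Protocol item | Definition example (6.2.1.3.5) | Solicited (Table 1) | Route by name in SAP 5.5.1.1 |
|---|---|---|---|
| Blister, vesicle | yes | yes | term: vesicles |
| Ulcerative lesion, ulceration | yes | yes | term: ulcer |
| Bleeding | yes | no | term: haemorrhage |
| Grade 4 reaction | yes | yes | verbatim search |
| Excoriation (erosion) | no | yes | none |
| Pruritus, erythema, oedema, urticaria, hyperpigmentation, eczema, pain | no | yes | none |

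Of the 11 solicited items, 3 have a route by name (ulceration, blister, Grade 4) and 11 − 3 = 8 do not. Seven of those eight are reactions that neither document presents as barrier-disrupting. The eighth is excoriation (erosion). All the definition's examples have a counterpart in the SAP, so the gap lies in the open-ended part of the definition.

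**Step 3: other routes into the count.**

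- *AESI form.* Protocol 6.2.1.3.5 bars its use for local events.
- *AESI tick box.* SAP 5.5.1.1 uses it to identify systemic AESIs. The local rule does not refer to it.
- *Grade 4 verbatim.* Protocol Table 3 defines Grade 4 as "Erythema and vesicles". An erosion without vesicles does not meet it.
- *Review of the list.* SAP 5.3.4 has the medical-history term lists reviewed at the data review meeting and allows them to be extended before lock. Protocol 6.2.1.3.5 has anaphylaxis cases found by algorithm confirmed by medical review. Neither provision is attached to the local AESI list.
- *Declared change.* SAP 5.11 records that AESI identification was updated but gives no reason for the choice of terms.

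**Step 4: what decides whether an event is lost.** The documents do not say which preferred term a patch-site erosion or excoriation is coded to. If it is a listed term such as injury, wound or ulcer, or if the verbatim mentions Grade 4, the event is counted. If it is a separate erosion or excoriation term, the event is not counted.

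**The case against.** The other side has a good deal to say, and most of it limits how far the point can go.

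- *Table 1 is a solicitation list, not an AESI list.* This stands. A reader might infer that excoriation is the only one of 11 solicited items without a match. In fact 8 of the 11 have none, and for most of them that is expected. The argument rests on the protocol's definition; solicitation shows only that the event will be asked about.
- *Excoriation is not among the protocol's examples.* This also stands. The protocol does not say that every excoriation is a local AESI; the test is whether the reaction could potentially lead to barrier disruption, which takes medical judgement. But the definition is explicitly not limited to its examples, and the SAP list itself goes beyond them (scab, scar, fissure, discharge, cyst). The SAP does not explain why those count and an erosion does not.
- *The loss depends on unseen coding.* This is correct, and it is why the claim is that events can be missed, not that they are.
- *Bias by arm.* A reader might infer that the reported rate is certainly too low, and mainly so in the active arm. The documents give no frequency of excoriation, no split by arm, and nothing on how often the same child would also have a listed term. That inference is not supported.
- *The events are not lost to the safety report.* This stands. SAP 5.5.1.3 tabulates all TEAEs by system organ class and preferred term, with administration-site conditions shown separately, and lists every event. If related and under the application-site high-level term, an event also counts as an IMP-induced local TEAE.
- *A fixed list set before unblinding is reproducible, and the change is declared.* Both true. Neither explains the omission, and a list can be fixed and complete at the same time.

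**Conclusion.** The point holds in a limited form. The SAP rule is narrower than the definition it implements, and it names no term for an event that sites actively solicit in Part B. No other route in the documents reliably closes the gap. If patch-site erosion or excoriation is coded outside the 15 terms and the verbatim does not mention Grade 4, qualifying events will be absent from the treatment-emergent local AESI count, and that count will be too low against the protocol definition.

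The size cannot be stated: neither the number of events nor the split by arm follows from the documents. The conclusion rests on two assumptions: that some such events meet the protocol's test, and that at least some are coded to an unlisted term. What is affected is the local AESI summary and its subgroup repeats, not the TEAE tables by preferred term and not the efficacy conclusion. It is worth correcting because the endpoint is named and the remedy is cheap.

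**What to change.** In SAP 5.5.1.1, add any application-site erosion and excoriation preferred terms that exist in the MedDRA version used (20.1 for this list). If they are deliberately left out, give the reason in SAP 5.11.

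Attach to this list the review already provided for the medical-history lists in SAP 5.3.4. At the blinded data review, compare every reported application-site preferred term with the definition in protocol 6.2.1.3.5, decide inclusion without knowledge of treatment, and record the final list before lock. This also settles how solicited excoriation was actually coded.

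The cost is a few added terms and a short blinded term review. The local AESI rate may rise slightly.

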#### *6.2.1.1 Collection of Adverse Events*

It is the responsibility of the Investigator to collect all AEs (both serious and non-serious) derived by spontaneous, unsolicited reports of subjects, by observation and by routine open questionings, for example "How have you felt since I last saw you?". Adverse events will also have to be recorded by the parents/guardians in the subject diaries (see Section 6.2.5).

The occurrence of the following AEs/symptoms will be specifically solicited:

- Pre-specified symptoms of local reactions at application site (itching, redness, swelling), by means of the subject diaries (during the first 6 months for part A, and during the whole treatment duration for part B; See also Section 6.2.5 regarding the rules of AEs reporting of these pre-specified local symptoms).

- Specific application site reactions and systemic events of a potential allergic nature (regardless of causal relationship with the IMP) will also be solicited at each study visit and phone contact for part B only (see Table 1).

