#### **Systemic AESIs:**

Systemic AESI is defined as any acute systemic immediate allergic reactions (rapid onset) after exposure to a known or suspected allergen regardless of the causal relationship to the IMP, and occurring outside the DBPCFCs. This includes:

1. Anaphylactic reaction
2. Any systemic hypersensitivity reaction leading to epinephrine intake

Systemic AESIs will be identified by the investigator in the eCRF using the tick box “AESI”.

In case of serious events and to avoid duplicated information, SAE form is completed instead of AESI form. Serious systemic AESIs will be identified as any SAE with a preferred term (PT) corresponding to:

- “Anaphylactic reaction”
- “Anaphylactic shock”
- (“Hypersensitivity” or “Food allergy”) AND AE leading to an epinephrine intake (Epinephrine use will be retrieved using Standard medication name containing “EPINEPHRINE” and ATC level 1 = “CARDIOVASCULAR SYSTEM”)

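### The SAP's closed rule for local AESIs names neither erosion nor excoriation, although the protocol solicits that reaction and defines local AESIs by possible skin-barrier disruption

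*SAP*

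**What the plan says.** Protocol 6.2.1.3.5 defines a local AESI openly: "Any reaction at patch application site which could potentially lead to a skin barrier disruption, such as but not limited to", followed by examples (blister, vesicle, ulcerative lesion, bleeding, any Grade 4 patch-site reaction). SAP 3.3 carries the same idea into the safety endpoint, describing local AESIs as "reactions at patch sites potentially leading to skin barrier disruption".

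Protocol Table 1 lists 11 application-site reactions for Part B. One of them is the item beginning "Excoriation (erosion". Under protocol 6.2.1.1 these reactions "will also be solicited at each study visit and phone contact for part B only".

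SAP 5.5.1.1 then fixes how local AESIs are found. The first route is "Any adverse events with a preferred term (PT) corresponding to this prespecified list of PT according to the MedDRA version 20.1", with 15 terms, among them "Application site scab". The second is a search of the verbatim for Grade 4 or Grade IV among events in the application-site high-level term.

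On data capture, the protocol instructs sites that "Local AESI should NOT be reported on the specific AESI form of the eCRF". In the SAP the investigator's flag belongs to the other category: "Systemic AESIs will be identified by the investigator in the eCRF using the tick box".

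**The concern.** The definition is open and the rule that implements it is closed. A sponsor may reasonably replace an open clinical definition with a programmable list, but the list should then cover the reactions that the protocol itself asks about and that fit the definition. An erosion is a loss of skin surface. If a scab, fissure, laceration or wound counts as potential barrier disruption, it is hard to see why an erosion would not.

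What is at stake is how one row of the adverse-event overview in SAP 5.5.1.3 reads. A reader will take that row as the rate of barrier-threatening patch reactions in children aged 1 to 3 who wear a patch every day. The overview is repeated by subgroup, with events from accidental peanut consumption included, and for treatment after the fourth birthday, so any omission carries into each repeat. An omitted term can only lower the row.

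**Working it through.** There is no planned figure to reproduce. The check sets the texts side by side.

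**Step 1: the 15 listed terms.** All begin with *Application site*: abscess, burn, cyst, discharge, extravasation, fissure, haemorrhage, injury, laceration, necrosis, scab, scar, ulcer, vesicles, wound. Terms naming erosion or excoriation: 0 of 15.

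**Step 2: the solicited reactions that describe broken or blistered skin** (4 of the 11 items in protocol Table 1).

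| Solicited item | Route in SAP 5.5.1.1 |
|---|---|
| Ulceration | *Application site ulcer* |
| Blister (vesicles) | *Application site vesicles* |
| Grade 4 reaction | Verbatim search |
| Excoriation (erosion) | None by name |

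**Step 3: other ways in.**
- The verbatim search needs the Grade 4 wording. Protocol Table 3 defines Grade 4 as erythema with vesicles, so an erosion alone has no reason to carry that wording.
- Local AESIs have no AESI form, and the SAP uses the tick box for systemic AESIs only.
- Protocol 6.2.1.3.5 plans medical review of retrieved cases for anaphylaxis, not for local AESIs.
- SAP 5.3.4 lets term lists be extended at the data review meeting, but this concerns medical history.
- SAP 5.11 says that AESI identification was updated, with no mention of erosion.

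**Step 4: when an event is actually missed.** A child drops out of the row only if all of these hold: the reaction codes to an unlisted preferred term, the verbatim lacks the Grade 4 wording, and the child has no other listed local event. The first condition depends on MedDRA coding that the documents do not show.

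**Step 5: scale.** The documents give no excoriation rate. With the planned Part B arms, each missed child lowers the active rate by 1/233 = 0.43 percentage points and the placebo rate by 1/117 = 0.85 points. Purely as assumptions for the share of children missed:

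| Assumed share | Active, of 233 | Placebo, of 117 |
|---|---|---|
| 0% (codes to a listed term) | 0 | 0 |
| 2% | 5 (2.1 points) | 2 (1.7 points) |
| 5% | 12 (5.2 points) | 6 (5.1 points) |
| 10% | 23 (9.9 points) | 12 (10.3 points) |

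Nothing in the documents selects a row of this table.

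**The case against.** **Coding may remove the problem.** Table 1 holds solicitation labels, whereas the SAP list holds MedDRA preferred terms. A word missing from the second list does not prove that an event is missing from the count. If the item codes to *Application site injury* or *Application site wound*, nothing is lost. This stands, and it is why the finding is conditional.

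**Excoriation is not a named local AESI.** The protocol's own examples each have a plausible route in the SAP, through vesicles, ulcer, haemorrhage and the Grade 4 search. Table 1 also contains itching, redness and hyperpigmentation, so being solicited does not make a reaction an AESI. A sponsor could want to keep scratch marks out so that they do not dilute graver lesions. This stands in part. Inclusion is a clinical reading of an open definition, though the presence of scab, fissure and wound on the list supports it. The readable text does not say that excoriation was left out deliberately.

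**Overlap and visibility.** A child whose excoriation also bled, scabbed or was reported as a wound may already be in the row. The events also remain in the tables by system organ class and preferred term and in the listings and, if related and coded as application-site reactions, among the IMP-induced local events. This stands and limits the consequence.

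**A stronger reading to avoid.** A reader might infer that the row understates the excess on active treatment, because pruritus is an expected reaction to DBV712 and the parents' diary ties severe itching to continuous scratching. Assuming 10% missed on active and 2% on placebo gives 23/233 − 2/117 = 9.87% − 1.71% = 8.2 points. The documents support neither rate. Protocol 6.2.6 also records whether patch removal injured the skin, a mechanism that could act in both arms. With 5% missed in each arm the difference changes by only 12/233 − 6/117 = 5.15% − 5.13% = 0.02 points.

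**Conclusion.** The mismatch in the text is real: the identification rule in SAP 5.5.1.1 is narrower than the endpoint in SAP 3.3, and it leaves out by name one of the four solicited reactions that describe broken or blistered skin. The local AESI row undercounts against its definition if two assumptions hold: that an erosion or excoriation counts as potential barrier disruption, and that at least some such events code to unlisted terms in children with no other listed local event. The documents settle neither the coding nor any rate, so the size may be zero and no between-arm effect can be claimed.

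The row is descriptive. No hypothesis test or success criterion depends on it, and the study stopping rules in protocol 4.3.2 rest on death, severe anaphylaxis and repeated epinephrine use. This is a minor point of definition, not a threat to the trial's conclusions.

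**What to change.** Before unblinding:

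1. Check which MedDRA 20.1 preferred term or terms excoriation (erosion) codes to.
2. If they are already on the list, state this in SAP 5.5.1.1; no other change is needed.
3. If they are not, add them to the list and show them as a separate sub-row, so that the local AESI rate can be read with and without them.
4. Record the addition in SAP 5.11.

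The cost is a coding check and, if needed, one or two terms in a programmed list and one table row. The drawback is that minor scratch marks would raise the local AESI rate in both arms; the sub-row makes that visible.
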